## Study Objectives

**Aim 1:** Examine the effectiveness of CR + tDCS to improve behavioral and neurophysiological measures of **cognitive control** among smokers with schizophrenia. Using a 2 X 2 factorial design (n=20 per group) we will examine main and interactive effects of CR and tDCS on multiple measures of cognitive control. Hypothesis: Combined CR + tDCS will result in greater improvement in MATRICS measures of cognitive control, as well as continuous performance task (CPT) relative to the other groups (CR + sham tDCS, AC + tDCS, AC + sham tDCS).

**Aim 2:** Determine the effectiveness of CR + tDCS to attenuate **reactivity to smoking stimuli** among smokers with schizophrenia. Hypothesis: CR + tDCS will lead to greater reductions in cue-induced craving, and improved reaction time and ERP measures of attentional bias relative to the other groups (CR + sham tDCS, AC + tDCS, AC + sham tDCS).

**Aim 3:** Examine if cognitive control enhancement (Aim 1) and/or changes in reactivity to smoking-related stimuli (Aim 2) predict reductions in measures of **actual smoking behavior**. Hypothesis: Enhanced cognitive control and attenuation of reactivity to smoking stimuli will be directly

related to reductions in smoking topography (i.e., Latency to light, puff volume, and number of puffs) within the CR + tDCS group.

**Secondary Aim:** To inform future clinical research, we will also explore whether changes in cognitive control and smoking reactivity measures are associated with changes in **quit intention** and **confidence in quitting** from baseline assessment to end of study by training condition.

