## Study design and methods

Using a 2 x 2 design we examined CR (CR, active control [AC]) X tDCS (active, sham) to enhance cognitive control, reduce cue-induced craving, and attenuate attentional bias measures of reaction time and ERPs to smoking stimuli; and, we determined the impact of these changes on smoking behavior and intent to quit and confidence in quitting among daily smokers with schizophrenia. Participants were assigned to active (2.0 mA) CR + tDCS, CR + sham (0.1 mA) tDCS, active control (AC) + active tDCS, or AC + sham tDCS, each with anode electrode placement over the right inferior frontal gyrus (IFG) and cathode electrode placement over the left bicep. Similar to our previous studies participants received 30 minutes of either active or sham tDCS during each visit, starting at the beginning of the CR training. AC consisted of a self-paced knowledge- and vocabulary-based task in which participants were given sequential multiple-choice questions about factual information at a 6th-grade level. Participants underwent consecutive CR + tDCS sessions, 5 days a week, for 2 weeks. Cognitive control, cue-induced craving and attentional bias (reaction time & ERPs), as well as smoking topography were assessed during Week1 baseline testing and Assessment Week 4.

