## Procedures and protocol

Eligible participants will be invited to the Clinical Neurophysiology Research Lab for informed consent and further screening, including CO, Smoking and Medical history, PANSS, Intention to quit, Confidence in quitting, and hearing/vision testing to screen for sensory problems that may affect cognitive and/or EEG testing. After initial screening on Day 1, participants will be randomized. Randomization for the 4 groups will be stratified by current typical or atypical antipsychotic medication to control for the potential interaction of tDCS with medication class. A randomization assignment list will be generated for each category using a permuted 4 block design. Dropouts will be replaced. Participants will then be scheduled for two baseline testing sessions, completed the same week as initial screening. The first will utilize the MATRICS Clinical Consensus Battery (MCCB) for baseline testing of cognitive measures. Participants will perform form A of the MCCB at baseline, which includes composite scores for attention, processing speed, working memory, and reasoning/problem solving. Participants will also complete behavioral tests of cognitive control, cue reactivity and attentional bias during this visit. Participants will then complete a baseline EEG testing session on a separate visit in the same week. Electrophysiological measures of cognitive control will be examined using the 'AX'-type Continuous Performance Task (AX-CPT). Cue-induced craving and smoking topography will be assessed with a pictorial cue reactivity paradigm, and attentional bias will be measured using a modified stroop task. Following baseline testing (Week1), participants will return 5 days (M-F) for the next 2 weeks for cognitive training with CR / tDCS and will receive the same tDCS condition in each visit. In week 4, participants will perform follow-up testing using form B of the MCCB, behavioral tests of cognitive control, cue-reactivity, and attentional bias on the first day, and EEG testing on the second.

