## Data Analysis

Prior to hypothesis testing, descriptive statistics and graphic displays will identify outliers and missing data and guide the use of transformations and appropriate tests. Correlation and principal component analysis will identify any outcomes reflecting the same underlying construct, and representative measures will be selected if necessary. We will use 2x2 ANOVA to assess the effects of tDCS (vs sham) and CR (vs AC) on pre-post change scores for all dependent variables. Should baseline differences be identified, post-training scores will be used as dependent variables, and baseline (pre-training) scores will be included as covariates in the analysis.

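### Dropouts are replaced after randomisation, and no Week 4 testing is stated for those who stop, so the 2x2 analysis in effect compares people with Week 4 data

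*Combined protocol and SAP*

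**What the plan says.** The order of events is in Procedures and protocol. On timing of assignment: "After initial screening on Day 1, participants will be randomized". After a sentence on the stratified assignment list comes: "Dropouts will be replaced. Participants will then be scheduled for two baseline testing sessions, completed the same week as initial screening". Dropout is not defined. The text does not say whether a replacement takes the same arm or the next list entry, or what happens to the replaced person's data.

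Follow-up is described for participants in general: "In week 4, participants will perform follow-up testing using form B of the MCCB". Nothing is said about those who stop training early. Study design and methods gives the period at risk: "Participants underwent consecutive CR + tDCS sessions, 5 days a week, for 2 weeks".

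The size is given under Aim 1, "Using a 2 X 2 factorial design (n=20 per group"), without saying whether it counts people randomised or people with outcomes.

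Data Analysis plans a 2x2 ANOVA "on pre-post change scores for all dependent variables". The alternative is conditional: "Should baseline differences be identified, post-training scores will be used as dependent variables", with baseline as covariate. Missing data appear once: "descriptive statistics and graphic displays will identify outliers and missing data and guide the use of transformations and appropriate tests". No analysis set or missing-data method is named.

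**The concern.** Randomisation protects the comparison of everyone assigned. It does not protect a comparison of those who reach Week 4. A change score and a baseline-adjusted Week 4 score both need the Week 4 value, so anyone without one falls out of either analysis.

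Suppose people leave more often at one level of CR or tDCS, and leaving is related to how they are changing. The estimated effect of that factor is then biased, in a direction the documents do not allow one to predict. Adding people until each group has 20 with data does not correct this. It can also make a report of 20 per group look complete when more were randomised and lost.

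Unequal dropout is plausible but not shown. A replacement rule implies that some dropout is expected, and training is ten 2-hour sessions. CR and the self-paced knowledge task are different experiences, as are 2.0 mA and 0.1 mA stimulation. Against that, the Interventions section equates time on task, describes tDCS as well tolerated, and reports that patients progress through the CR exercises. None of this gives dropout by arm.

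**Working it through.** **From the documents.** 4 groups x 20 = 80, so 40 per factor level. Randomisation is on Day 1 and the outcome is at Week 4. No dropout rate, alpha, power, effect size or SD is stated, so the 20 per group cannot be reproduced.

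**Assumed.** Dropout d of 10%, 20% or 30%; correlation r of 0.3 to 0.5 between change and the latent tendency to stay; pre-post correlation 0.5 to 0.7; two-sided 5% test; no true effect. Units are SDs of change.

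**Step 1: bias of the change-score comparison.** The mean change among those retained shifts by r x phi(z_d)/(1 − d), where z_d is the normal quantile at d.
- phi(z_d)/(1 − d) = 0.195 (10%), 0.350 (20%), 0.497 (30%).
- 20% v 20%: bias 0.
- 20% v 10%: 0.3 x 0.155 = 0.046; 0.5 x 0.155 = 0.077.
- 30% v 10% (stress case): 0.3 x 0.302 = 0.091; 0.5 x 0.302 = 0.151.

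**Step 2: false-positive rate.** For a main effect, SE = sqrt(2/40) = 0.22. The noncentral t with 76 df and retained-group variances gives 5.5% to 6.5% at 20% v 10%, and 6.9% to 10.8% at 30% v 10%. Aims 1 and 2 compare CR + tDCS with the other groups. For 20 v 20, SE = sqrt(2/20) = 0.32, and the same biases with unit variance give about 5.2–5.7% and 5.9–7.6%.

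**Step 3: what replacement itself adds.** Without replacement, 30% v 10% gives 6.5% to 9.5%. Replacement therefore adds 6.9 − 6.5 = 0.4 to 10.8 − 9.5 = 1.3 points.

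**Step 4: alternatives, with dropout driven by change** (large simulation, bias in SD).

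| Analysis | 20% v 10% | 30% v 10% |
|---|---|---|
| Change score, those with Week 4 data | 0.05–0.08 | 0.09–0.15 |
| Baseline-adjusted, those with Week 4 data | 0.035–0.07 | 0.07–0.13 |
| Missing-at-random imputation from baseline, all randomised | 0.035–0.07 | 0.07–0.13 |
| Random half of those who stop tested, baseline-adjusted | 0.014–0.026 | 0.03–0.05 |
| Less dropout-prone half tested, baseline-adjusted | not tabulated | 0.04–0.07 |

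With a single follow-up and baseline as the only covariate, imputation matches the adjusted analysis of those with data.

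**Step 5: dropout driven by baseline only.** The change score is biased by 0.02–0.08 SD in the opposite direction. The adjusted model has bias 0.00.

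**Step 6: precision of adjustment.** With pre-post correlation rho, the residual variance relative to a change score is (1 − rho²)/(2(1 − rho)) = (1 + rho)/2. This is 0.75 at rho = 0.5 and 0.85 at rho = 0.7, a reduction of 25% to 15%.

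**Step 7: numbers.** Reaching 20 per group with outcomes needs 4 x ceil(20/(1 − d)) = 92, 100 or 116 randomised at equal losses of 10%, 20% or 30%. Without additions the main-effect SE, sqrt(2/(40(1 − d))), rises from 0.22 to 0.24, 0.25 or 0.27.

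**The case against.** The best counter-argument is that the replacement sentence is not the real fault. It adds at most 1.3 points to the false-positive rate, even in the stress case. It could also be read narrowly, as covering losses before training only, and replacing those would be harmless. This stands: a reader might infer that replacement causes the bias, and it does not. The gap is the absence of a follow-up rule and an analysis set; replacement only conceals the result.

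A reader might also infer that the plan prescribes a completers-only analysis or excludes those who stop from Week 4. The documents say neither. Week 4 testing is described for participants without restriction, and the rest is inference from silence in the available text.

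The size is modest and rests wholly on assumed rates. That also stands, and the effect is smaller still for 20 v 20 comparisons.

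Nor does drawing the assignment on Day 1 bias anything by itself. An equal 15% loss in the baseline week with the arm unknown gives bias 0.00. The available text does not say whether participants know their arm by then.

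Finally, multiple imputation or a likelihood method looks like the obvious remedy. Step 4 shows that with baseline alone it gains almost nothing over the covariate model the plan already contains. Week 4 testing of those who stop is the stronger protection, but its benefit depends on who returns.

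**Conclusion.** The concern holds in a limited form. As written, the 2x2 comparison is in effect of people with Week 4 data, and replacement neither removes the resulting bias nor lets a reader see it. Under the assumed inputs the main-effect bias is 0.05–0.08 SD at 20% v 10% dropout and 0.09–0.15 SD in the 30% v 10% stress case. It is zero with equal dropout and mechanism. Direction cannot be predicted, and no bias has been shown to exist in this trial. The change is worth making because it is cheap and one does not then have to rely on equal dropout. Confidence is medium, because the dropout figures are assumptions and parts of the document were not available.

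**What to change.** 1. **Procedures.** Replace the replacement sentence with: *All randomised participants stay in their assigned group. Those who stop training are still invited to both Week 4 sessions, and every available Week 4 score is analysed. An added participant takes the next entry on the stratum's list and displaces no one.* Define dropout, recording stopping training separately from missing Week 4 testing.
2. **Data Analysis.** Use the 2x2 model for the Week 4 score with baseline as covariate in all cases, not only when baseline differences are seen. State that it removes bias when dropout depends on baseline only and leaves most of it when dropout depends on change. Likelihood or imputation from baseline alone is optional.
3. **Sensitivity.** For one main cognitive-control outcome, named in advance, shift the missing Week 4 scores in both directions, in both factor levels and in one at a time. A range of −1.0 to +1.0 SD of change in steps of 0.25 is wide enough: in the 30% v 10% case a common shift of 0.35–0.66 SD cancels the residual bias. Report the shift at which the conclusion changes.
4. **Reporting.** Give numbers randomised, lost by week, added and analysed, per arm.

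Optional, if recruitment is open: draw the assignment after the second baseline session. Medication class, the stratifier, is known at screening, so this costs a few days.

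**Cost.** If 20% stop and half return, 10% lack outcomes, so 92 rather than 100 are randomised. About 18 of the 92 stop and 9 return for 2 sessions each, which is about 18 extra visits. Using the next list entry will not give exactly 20 per group if losses are unequal: 25 randomised per group gives 17.5 v 22.5 at 30% v 10%. Some people will refuse testing, so a missing-data assumption remains. The analysis work is small. Study design and methods is written in the past tense; if conduct is finished, items 2 to 4 and the use of every available Week 4 score still apply.

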## Measures.

### **Cognitive Control:**

**MATRICS Clinical Consensus Battery (MCCB).** An abbreviated MCCB will be completed before and after CR + tDCS. Subscales include: Attention: The Continuous Performance Test (CPT), the Continuous Performance Test—Identical Pairs (CPT-IP), and the A-X Continuous Performance Test (AX-CPT). Working memory: N-Back digit sequencing from the BACS, Spatial span from the Wechsler Memory Scale, 3rd ed. (WMS-III), Letter-number sequencing from the WAIS-III, Spatial delayed response task. Reasoning/problem solving: Block design from the WAIS-III, Tower of London from the BACS, Mazes and Categories from the Neuropsychological Assessment Battery, Penn Conditional Exclusion Test, Sorting test from the Delis-Kaplan Executive Functioning Scale. To reduce practice effects, two forms are available for most measures.

**The Continuous Performance Test (CPT)** is a go/no-go task requiring continuously responding to frequent stimuli, and withholding response to a rare target stimulus. EEG will be recorded this task. The AX-CPT also requires maintaining stimulus items in temporary memory store (respond to the letter 'X' only when it follows the letter 'A'). The AX-CPT can measure *proactive cognitive control* of response inhibition. Additionally, a negative ERP, a contingent negative variation (CNV), and a reduction in beta-band oscillations compared to baseline (event-related desynchronization (ERD)), occur between the alerting stimulus ("A") and target stimulus ("X"). Both are blunted in schizophrenia patients and this proactive control deficit may be part of problematic cognitive coordination in schizophrenia.

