### **Smoking-related reactivity.**

**Attentional Bias (Reaction time and ERPs)** Participants will be seated in front of a computer with a four-button color response box. Four-word lists (two neutral and two smoking-related) of 15 words each, will be presented in a random order with no repeat. For each trial, a cross appears in the center of the screen for 500ms followed by one word from the list in one of the four colors. Participants respond by pressing the color button that matches the color in which the word appears. Reaction time to respond to each word is recorded within the nearest ms. These procedures are similar to those used

in a past modified-stroop test with smokers. We will also examine EEG correlates of smoking reactivity. In past studies, smokers have increased electrophysiological responses to smoking compared to neutral images, such that their N200 and P300 ERPs are larger in response to smoking stimuli. We will assess this response before and after CR + tDCS to examine neural correlates of attentional bias related to increased N200 and P300 in smokers.

**Cue-Induced craving and smoking topography.** Participants' reactivity to smoking-related cues will also be assessed at Baseline and Week 4 Assessments. To equate time to last cigarette, participants will light a cigarette and smoke as much or as little as they like prior to each the testing session. Cue reactivity testing is computer automated. Following a practice trial, the participant will be viewed by the experimenter on a monitor outside of the subject room to verify compliance with instructions (sit back, focus on pictures, and fill out ratings), which appear on the screen. Four angles of each pictorial cue will be presented for 4 smoking and 4 nonsmoking picture trials with self-report ratings in between. Each cue trial will end with a computer prompt for subjects to complete post-trial craving ratings on a 0-100 scale (4-item Questionnaire on Smoking Urges) After the ratings are filled out for the last cue-reactivity trial, a screen will appear informing subjects that when the pictures return they may smoke as much or as little as they like. They will then complete a 10-minute ad lib smoking / cue-viewing period during which all smoking will occur through a CReSS cigarette holder, allowing for topographical assessment of latency to light, puff volume, and number of puffs.

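### Does the Secondary Aim lack a post-training measurement of quit intention and confidence in quitting?

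*Combined protocol and SAP*

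**What the plan says.** The combined protocol and SAP treats the two quit outcomes in four places.

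- **Study Objectives, Secondary Aim.** It explores whether changes in cognitive control and smoking reactivity go with changes in quit intention and confidence "from baseline assessment to end of study by training condition". Its stated purpose is to inform later research.
- **Study design and methods.** In the past tense: "we determined the impact of these changes on smoking behavior and intent to quit and confidence in quitting". The sentence on repeated assessments lists cognitive control, craving and attentional bias, "as well as smoking topography were assessed during Week1 baseline testing and Assessment Week 4". It does not name the quit outcomes.
- **Procedures and protocol.** Participants attend "for informed consent and further screening, including CO, Smoking and Medical history", and that list goes on to include both quit questionnaires. Randomization comes after this Day 1 screening. For follow-up: "In week 4, participants will perform follow-up testing using form B of the MCCB, behavioral tests of cognitive control, cue-reactivity, and attentional bias". These tests fill the earlier of two Week 4 visits; the later one is for EEG.
- **Data Analysis.** A 2 x 2 ANOVA is applied "on pre-post change scores for all dependent variables".

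The Measures section has no entry for either questionnaire. It does give timing for other outcomes, for example "An abbreviated MCCB will be completed before and after CR + tDCS".

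**The concern.** A change score needs two measurements, and the visit descriptions supply one. Brevity alone does not obviously explain the omission, because the other outcomes named in the aims are placed at Week 4 or after training somewhere in the text. The two quit outcomes are the only ones that no visit description picks up.

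If staff gave only what the narrative lists, the Secondary Aim would have no post-training value, and a self-reported state cannot be recovered afterwards. If the forms were given at an unstated visit, a reader could not tell whether they came before or after the cue task and the smoking period that ends it. On Day 1 no cue task precedes them, so the two measurements could have been taken under different conditions.

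**Working it through.** There is no formula to reproduce. The check sets each outcome named in Study Objectives against every place where the available text gives it a post-training time.

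| Outcome | Where a post-training time is given |
|---|---|
| MATRICS measures | Procedures (form B in Week 4); Measures (before and after training) |
| CPT | Study design (cognitive control at Week 4); Procedures |
| Cue-induced craving | Study design; Measures: "reactivity to smoking-related cues will also be assessed at Baseline and Week 4 Assessments" |
| Attentional bias, reaction time | Study design; Procedures |
| Attentional bias, ERP | Study design; Procedures (EEG, second day); Measures |
| Smoking topography | Study design; Measures (same cue paradigm) |
| Quit intention | Secondary Aim only: end of study |
| Confidence in quitting | Secondary Aim only: end of study |

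**Tally.** Six of the eight outcomes have an assessment occasion in the procedural text, and 8 − 6 = 2 do not. The split depends on grouping: counting the three topography measures separately gives 8 − 1 + 3 = 10 outcomes, of which 8 are placed and the same 2 are not.

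**Is a second measurement required?** Yes, on three counts. The Secondary Aim defines the change as running to the end of the study. Data Analysis applies change scores to all dependent variables. The design section says the effect on both outcomes was determined. None of these can be met from Day 1 alone.

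**Which visit can the end of study be?** The contacts described are screening and baseline testing in Week 1, training on 5 days a week for 2 weeks (5 × 2 = 10 sessions), and two assessment days in Week 4. The two Week 4 days are the only contacts after training. A training day that precedes them is not a natural reading. What remains open is which of the two days, and the order within it.

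**Is the Day 1 value a usable baseline?** Yes. It is taken before randomization and in the same week as the baseline testing sessions.

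**How large could the loss be?** With 4 × 20 = 80 planned participants, the number of available change scores lies somewhere between 0 and 80. That range only restates that the visit is unnamed, and it estimates nothing. The lower end also sits badly with the design section's statement that the effect was determined.

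**The case for a change.** The strongest case for acting is that intention does not assign a visit. Staff work from procedures, the procedures name these forms once, and adding two short questionnaires to an existing visit costs almost nothing. Order could also matter. The first Week 4 day includes cue-reactivity testing that closes with 10 minutes of free smoking. Forms completed after it could carry a passing state that also affects the craving ratings, and the aim relates changes in those two sets of measures.

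Part of this stands. No available text names the visit, and a reader of the Secondary Aim results will want to know the visit and the order.

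The rest is weaker. The Procedures section is a narrative summary, not a schedule of assessments. Its Week 4 sentence works by headings: the cue-reactivity heading takes in craving and topography, because the same section says both are assessed with that paradigm, and EEG takes in the ERPs. A sentence written at that level is poor evidence that two brief questionnaires were left out on purpose. An order applied alike in all four groups would not by itself favour one of them. The design section is also in the past tense: if collection is complete, adding the forms to its list of repeated assessments would change no data and would assert something the text does not establish.

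**Conclusion.** The omission is real but small: 2 of 8 named outcomes lack a visit label, both belonging to one exploratory aim. The time point itself is given, and the plan read as a whole already requires the second measurement at Week 4. This is a gap in description that staff and analysts would fill sensibly, so no change to the plan is called for. The report of the Secondary Aim can state which Week 4 day was used and whether the forms came before or after the cue task. If no second value was obtained, it can say that the aim could not be assessed.

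The conclusion assumes that the end of the study means Week 4, which is the only reading that fits the described contacts, and that the forms were given alike in all groups. The documents do not show whether the Week 4 values were collected, and some pages were not available to check. Aims 1 to 3 do not use either questionnaire and are unaffected in any case.
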